3.5.2. Laboratory Data

Laboratory data includes hematology, chemistry, and other safety tests. To determine if there are any clinically significant laboratory abnormalities, the hematological and chemistry and other safety tests will be assessed against the criteria specified in the Pfizer reporting standards. This assessment will take into account whether each participant's baseline test results are within or outside the laboratory reference range for particular laboratory parameter.

3.5.3. Vital Signs

Vital sign measurements, including temperature, pulse rate, respiratory rate, oxygen saturation level, and blood pressure.

4. ANALYSIS SETS (POPULATIONS FOR ANALYSIS)

Data for all participants will be assessed to determine if participants meet the criteria for inclusion in each analysis population prior to unblinding and releasing the database and classifications will be documented per standard operating procedures.

Population	Description
Full analysis set (FAS)	All participants randomly assigned to study intervention.
Safety analysis set (SAS)	All participants randomly assigned to study intervention and who take at least 1 dose of study intervention. Participants will be analyzed according to the study intervention they received.
mITT	All participants randomly assigned to study intervention who take at least 1 dose of study intervention and who have a positive viral RNA NP swab test result ($\geq 2.0 \log_{10}$ copies/mL) at baseline. Participants will be analyzed according to the study intervention they were randomized.
Per protocol (PP)	All participants in the mITT analysis set without important protocol deviations considered to impact the interpretation of the primary efficacy endpoint. Protocol deviations will be reviewed to generate the list of participants with significant deviations to be excluded from the PP analysis set. The PP exclusion criteria will be finalized prior to breaking the blind.
mITT1	All participants randomly assigned to study intervention who take at least 1 dose of study intervention and who have a positive rapid antigen test result at baseline. Participants will be analyzed according to the study intervention they were randomized.

The primary analysis set for efficacy will be the mITT. mITT1 will be used for relevant efficacy endpoints. Safety Analysis Set (SAS) will be used in the analyses of the safety data.

All participants from CCI [REDACTED] will be excluded from the efficacy analyses due to GCP issues.

5. GENERAL METHODOLOGY AND CONVENTIONS

5.1. Hypotheses and Decision Rules

The primary hypothesis is to test whether or not there is a difference in mean change of viral RNA level in NP swabs from baseline to Day 5 between nirmatrelvir/ritonavir and the placebo/ritonavir group:

Null hypothesis: $H_0 \quad \mu_{\text{nirmatrelvir/ritonavir}} - \mu_{\text{placebo/ritonavir}} = 0$

Alternative hypothesis: $H_a \quad \mu_{\text{nirmatrelvir/ritonavir}} - \mu_{\text{placebo/ritonavir}} \neq 0$

Where $\mu_{\text{nirmatrelvir/ritonavir}}$ and $\mu_{\text{placebo/ritonavir}}$ are mean change of viral RNA level (\log_{10} copies/mL) in NP swabs from baseline to Day 5 for nirmatrelvir/ritonavir and placebo/ritonavir groups.

The overall Type I error rate across the primary and key secondary efficacy endpoints will be controlled at alpha = 0.05. Following the positive test of the primary efficacy endpoint in the primary analysis set (mITT), the secondary analysis for the primary efficacy endpoint using the mITT1 analysis set will be tested.

Following the positive test of the secondary analysis, the following key secondary efficacy endpoints will be tested using Hochberg method:¹

- Time to 2 consecutive negative rapid antigen test results obtained at least 24 (-2)h apart through Day 28 in the mITT analysis set.
- Time (days) to sustained alleviation of all targeted signs and symptoms through Day 28 where sustained alleviation is defined as the first of two consecutive days when any symptoms scored as moderate or severe at baseline are scored as mild or absent and any symptoms scored as mild or absent at baseline are scored as absent in the mITT analysis set.

5.2. General Methods

Baseline demographic and other characteristics will be tabulated for the FAS and summarized by treatment group. Quantitative variables will be described by standard descriptive statistics and qualitative variables will be summarized by frequency tables with number and proportion in each category.

5.2.1. Analyses for Binary Endpoints

For binary endpoints, the proportion of participants with the event will be summarized for each group. Where appropriate, logistic regression will be utilized to estimate the odds ratio and its corresponding 95% confidence interval.

5.2.2. Analyses for Continuous Endpoints

For continuous endpoints, descriptive statistics will be provided by treatment group. Where appropriate, analysis of covariance (ANCOVA) or mixed model for repeated measures (MMRM) analysis will be utilized.

5.2.3. Analyses for Categorical Endpoints

For categorical endpoints, the number and proportion of participants for each category will be summarized for treatment group.

5.2.4. Analyses for Time-to-Event Endpoints

For time-to-event endpoints, a Cox proportional hazard regression model will be performed and the estimate of the hazard ratio, its confidence interval and p-value will be provided. In addition, time-to-event endpoints will be summarized graphically using Kaplan-Meier plots for each treatment group.

5.3. Methods to Manage Missing Data

Missing viral load will not be imputed in general. MMRM will be used to analyze viral load data to handle Missing at Random (MAR), and it allows for inclusion of participants with partial longitudinal data in the analysis.

For safety data, missing and partial dates will be programmatically handled according to Pfizer standards.

6. ANALYSES AND SUMMARIES

6.1. Primary Endpoint(s)

The primary efficacy endpoint is the change in viral SARS-CoV-2 RNA level from baseline to Day 5 as measured in NP swabs.

6.1.1. Main Analysis

The primary analysis for mean change in SARS-CoV-2 RNA level from baseline will be performed using a MMRM. The analysis will include the fixed effects of treatment, geographic region, baseline viral RNA level, visit, and treatment-by-visit interaction. An unstructured (co)variance structure will be used to model the within-participant variability. The LS means and treatment difference for each visit will be calculated and presented with their corresponding 95% CIs. The primary comparison for treatment effect will be the difference in LS means and 95% CI at Day 5. The primary analysis will be performed using mITT analysis set.

The secondary analysis for primary endpoint will be performed using the mITT1 analysis set. In the analysis, samples with result “<LLOQ” will be imputed as $1.7 \log_{10}$ copies/mL, and samples with result “undetectable” will be imputed as $0.0 \log_{10}$ copies/mL.

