2.1. Study Rationale

Case reports in the literature describe individuals who have experienced symptomatic relapses of SARS-CoV-2 infection following completion of a 5-day course of nirmatrelvir/ritonavir[1-3]. In the available cases, patients are described as experiencing rapid improvement in systemic symptoms following initiation of treatment but then experience a rebound in COVID-19 symptoms after completing therapy. The time course of symptom rebound suggests that symptom recurrence is likely not related to re-exposure and that it does not reflect a potential re-infection event. In one case report, symptom relapse was accompanied by fluctuating RT-PCR cycle thresholds and antigen testing suggesting the potential for a rebound in viral replication. In a separate case series of 7 patients with recurrent symptoms, median SARS-CoV-2 RNA at baseline was $6.1 \log_{10}$ copies/mL (range 4.2-7.3) and enrollment viral cultures were positive in 3 of 7 individuals[4]. Several of the published case reports on symptom recurrence included viral sequencing and these reports to date have not identified resistance mutations to nirmatrelvir.

A retrospective review of 483 high-risk patients treated with nirmatrelvir/ritonavir reported 4 (0.8%) of patients experienced rebound of symptoms. Median time to rebound was reported as 9 days. Rebound symptoms were characterized as mild and resolving without additional COVID-19 therapy with no patient requiring hospitalization[5].

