9. STATISTICAL CONSIDERATIONS

Detailed methodology for summary and statistical analyses of the data collected in this study is outlined here and further detailed in the SAP, which will be maintained by the sponsor. The SAP may modify what is outlined in the protocol where appropriate; however, any major modifications of the primary endpoint definitions or their analyses will also be reflected in a protocol amendment.

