2.4. Sample Size Determination

The study will enroll approximately 411 participants.

The sample size calculation is based on the primary efficacy endpoint as the change in viral RNA level from baseline to Day 5 as measured in NP swabs in the MITT analysis set. Assuming a SD of 1.8 (based on EPIC-HR, NCT04960202), a sample size of approximately 315 evaluable participants (210 participants in nirmatrelvir/ritonavir group and 105 participants in placebo/ritonavir group) is expected to provide 90% power to detect a difference of 0.7 \log_{10} copies/mL in viral RNA between groups using a 2-sided 0.05 alpha level test. Assuming approximately 10% of participants will have a negative viral RNA result at baseline, and assuming a non-evaluable rate of 15%, approximately 411 participants will be randomized in the study to achieve approximately 315 participants evaluable for the primary efficacy endpoint.

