6.3. Tertiary/Exploratory Endpoints

6.3.1. Proportion of Participants with SARS-CoV-2 RNA in NP Swab below the LLOQ on Days 3, 5, 10, 15, 21, 28, and 34

The number and proportion of participants with SARS-CoV-2 RNA level in NP swabs $<2.0 \log_{10}$ copies/mL at 3, 5, 10, 15, 21, 28, and 34 will be summarized by treatment group. The analysis will be done using mITT analysis set.

6.3.2. Proportion of Participants with Sustained NP Swab SARS-CoV-2 RNA below the LLOQ (defined as $<2.0 \log_{10}$ copies/mL) from Day 5 through Day 34

The number and proportion of participants with sustained NP swab SARS-CoV-2 RNA $<$ LLOQ (defined as $<2.0 \log_{10}$ copies/mL) from Day 5 through Day 34 will be summarized by treatment group using mITT analysis set.

Sustained SARS-CoV-2 RNA below the LLOQ from Day 5 through Day 34 is defined as having all non-missing measurements from Day 5 to Day 34 below the LLOQ and no more than 3 visits with missing SARS-CoV-2 RNA levels (scheduled collection on Days 5, 10, 15, 21, 28 and 34).

6.3.3. Proportion of Participants with SARS-CoV-2 RNA in NP Swabs below the LLOQ (defined as $<2.0 \log_{10}$ copies/mL) on both Days 5 and 10

The number and proportion of participants with SARS-CoV-2 RNA in NP swabs below the LLOQ (defined as $<2.0 \log_{10}$ copies/mL) on both Days 5 and 10 will be summarized by treatment group. The analysis will be done using mITT analysis set.

6.3.4. Change in SARS-CoV-2 RNA Level in NP Swabs from Baseline to Days 3, 10, 15, 21, 28, and 34

Change in SARS-CoV-2 RNA level in NP swabs from baseline to Days 3, 10, 15, 21, 28, and 34 will be analyzed similarly to the primary endpoint using MMRM model in the mITT analysis set. The LS means and treatment difference for each visit will be calculated and presented with their corresponding 95% CIs.

6.3.5. Time to Sustained NP Swab SARS-CoV-2 RNA below the LLOQ (defined as $<2.0 \log_{10}$ copies/mL) and Remains below the LLOQ through Day 34 for Participants with NP Swab SARS-CoV-2 RNA Greater than or Equal to the LLOQ at Baseline

Time to sustained NP swab SARS-CoV-2 RNA below the LLOQ (defined as $<2.0 \log_{10}$ copies/mL) and remains below the LLOQ through Day 34 will be summarized graphically using Kaplan-Meier plots for each of the treatment groups. The analyses will be done similarly as in Section 6.2.2 using the mITT analysis set, which includes participants with baseline viral load \geq LLOQ.

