6.3.8. Change from Baseline in SARS-CoV-2 Viral RNA Level in Plasma, Over Time

Change from baseline in SARS-CoV-2 viral RNA level in plasma, over time will be analyzed similar to the primary endpoint using MMRM model in mITT analysis set. The LS means and treatment difference for each visit will be calculated and presented with their corresponding 95% CIs.

6.3.9. Proportion of Participants with COVID-19-related Hospitalization >24h or Death from Any Cause through Day 28

The number and proportion of participants with COVID-19-related hospitalization >24h or death from any cause through Day 28 will be summarized by treatment group. The analyses will be done using the mITT analysis set.

6.3.10. Number of COVID-19-related Medical Visits through Day 34

Number of COVID-19-related medical visits through Day 34 will be summarized by treatment group descriptively (n, mean, standard deviation, median, min, max). The analysis will be done using the mITT analysis set.

6.3.11. Time (days) to Sustained Resolution of All Targeted Signs and Symptoms through Day 28

Sustained resolution of all targeted COVID-19 signs/symptoms is defined as the event occurring on the first of 2 consecutive days when all targeted COVID-19 symptoms are scored as absent. The first day of the 2 consecutive-day period will be considered the First Event Date.

For symptoms with no reported severity in baseline, the symptom will have to be absent in order to be counted as sustained resolution (missing severity at baseline will be treated as mild).

Day 27 is the last possible day that symptom resolution can be achieved (definition includes data from the subsequent day) and Day 28 is the last day participants report their daily signs and symptoms.

The time to sustained symptom resolution for the purpose of this study is defined as:

- For a participant with sustained symptom resolution, time to event will be calculated as (First Event Date) – (First Dose Date) +1.
- For a participant that either completes Day 28 of the study or discontinues from the study before Day 28 without sustained symptom resolution (censored), censoring date will be at the last date on which symptom resolution is assessed, and time will be calculated as (Censoring Date) – (First Dose Date) +1 or Day 27 whichever occurs first.

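### The primary MMRM has no baseline-by-visit term and no list of visits; if it is fitted through Day 34, the Day 5 comparison probably loses some precision

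*SAP*

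**What the plan says.** SAP 6.1.1 and Protocol 9.3.2.2 give the same primary model: "The analysis will include the fixed effects of treatment, geographic region, baseline viral RNA level, visit, and treatment-by-visit interaction". SAP 6.1.1 adds: "An unstructured (co)variance structure will be used to model the within-participant variability". The primary contrast is the Day 5 difference in LS means. Baseline RNA appears as a main effect only.

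Neither section lists the visits in the fit. Both ask for LS means at each visit. NP swabs are scheduled at Days 3, 5, 10, 15, 21, 28 and 34. SAP 6.3.4 says that the change in NP RNA "from baseline to Days 3, 10, 15, 21, 28, and 34 will be analyzed similarly to the primary endpoint using MMRM model". SAP 6.3.8 reuses the model for plasma RNA, which "will be analyzed similar to the primary endpoint using MMRM model in mITT analysis set". SAP 5.3 chooses MMRM partly because "it allows for inclusion of participants with partial longitudinal data in the analysis".

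SAP 6.1.1 sets results below the LLOQ to 1.7 and undetectable results to 0.0 log10 copies/mL.

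**The concern.** One baseline slope must serve every visit. At Day 5 many participants still have quantifiable virus, so change depends only in part on baseline. By the late visits most samples probably sit at a floor value. Change is then a constant minus baseline, and its slope on baseline is close to -1.

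Late visits also scatter little around that line, so with unstructured covariance they weigh heavily in the common slope. The Day 5 difference is then adjusted with a slope that does not fit Day 5. Adjustment meant to gain precision gains less than it could, or even loses precision.

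The Day 5 test in the mITT set gates the mITT1 test and then both key secondary endpoints (SAP 5.1), so lost power there carries through the whole sequence. The missing visit list matters in its own right: two programmers could fit different visit sets and report different primary p-values.

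**Working it through.** **The plan's own figure.** SAP 2.4 has 210 and 105 evaluable participants, difference 0.7, two-sided alpha 0.05, and "Assuming a SD of 1.8 (based on EPIC-HR, NCT04960202".
- SE = 1.8 × √(1/210 + 1/105) = 0.2151.
- 0.7/0.2151 = 3.254, so power = Φ(3.254 − 1.960) = 0.902.
- 315/(0.90 × 0.85) = 411.8, against 411 stated.

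The 90% and the sample size reproduce from a two-sample formula without covariates.

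**Variance of the Day 5 estimate (complete data).** Let b be the slope used, b5 the Day 5 slope, varB the baseline variance and σ the SD of Day 5 change.
- Estimate = difference in mean change − b × difference in mean baseline.
- Its variance is proportional to (σ² − b5²·varB) + (b − b5)²·varB.
- Ratio to the model with a Day 5 slope = 1 + (b − b5)²·varB/(σ² − b5²·varB).
- For slopes of the same sign, the variance exceeds that of no baseline adjustment once |b| > 2|b5|.

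**Worked cases** (σ = 1.8 taken as raw; slopes and baseline SD assumed; normal approximation):

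| Baseline SD | b5 | b | Ratio | Power, Day 5 slope | Power, common slope |
|---|---|---|---|---|---|
| 1.5 | -0.4 | -0.8 | 1 + 0.36/2.88 = 1.13 | 0.93 | 0.90 |
| 1.5 | -0.4 | -0.95 | 1 + 0.681/2.88 = 1.24 | 0.93 | 0.87 |
| 1.15 | -0.25 | -0.95 | 1 + 0.648/3.157 = 1.21 | 0.91 | 0.85 |
| 1.15 | -0.4 | -0.6 | 1 + 0.053/3.028 = 1.02 | 0.92 | 0.92 |

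**Where the common slope lands.** Under unstructured covariance, b = 1'S⁻¹b_v / 1'S⁻¹1, where b_v are the visit slopes and S is the residual covariance. This was evaluated over 342 sets of assumed inputs:
- Baseline mean 6.1, the median in Protocol 2.1 ("In a separate case series of 7 patients with recurrent symptoms").
- Baseline SD 1.15 to 1.8; the lower value is the range 4.2 to 7.3 in those 7 patients, 3.1/2.70 = 1.15.
- Baseline reliability 0.6 to 0.95, lognormal decay rates, 0 to 12% slow clearers.
- 85 to 99% of samples at the floor by Day 34, with 30 to 99% of those undetectable.
- Decay spread and treatment effect tuned to an SD of 1.8 and a Day 5 difference of 0.7.

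Results for a fit through Day 34:
- Common slope -0.42 to -0.97, against a Day 5 slope of -0.04 to -0.55.
- Variance ratio 1.03 to 1.48, median 1.13; above 1.3 in 7% of sets.
- Power 0.77 to 0.92 (median 0.88), against 0.90 to 0.96 with the interaction: a loss of 0.8 to 13.5 points, median 3.3.
- Under 94% at the floor by Day 34: ratio 1.03 to 1.20, loss 0.8 to 5.8 points. At 94% or more: 1.06 to 1.48, loss 1.3 to 13.5 points.

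The ratio is 1.00 to 1.25 (median 1.01) for a fit through Day 15, and 1.00 to 1.05 (median 1.00) through Day 10.

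**Finite-sample check.** Six grid points were simulated with 2500 replicates each, 246/124 in the mITT set (411 × 0.9 = 370) and 12 to 13% missing at Day 5 with MAR dropout. Mean estimates of the two models agreed within 0.003. Type I error was 0.046 to 0.055 as written and 0.044 to 0.054 with the interaction. The empirical variance ratio was 1.06 to 1.45, and power was 0.80 to 0.93 against 0.92 to 0.95.

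**Separate simulation, other assumed inputs** (210:105, 150 to 400 replicates per scenario). With a light or moderate floor the ratio was 0.99 to 1.10. With a heavy floor (85 to 90% below the LLOQ at Day 10, at least 96% from Day 15) the common slope reached -0.95 to -1.00, against -0.13 to -0.40 at Day 5. The ratio was then 1.18 to 1.57, and 2.2 in one extreme case. At 1.57, power was 0.783 as written and 0.927 with the interaction.

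**The case against.** The strongest reply is that nothing here is an error. The model is valid, a main-effect baseline covariate is a legitimate prespecified choice, and 315 was derived without covariate adjustment. If 1.8 is a raw SD, median power as written is 0.88 against a planned 0.90. The 3.3-point median loss is measured against a better model than the one the trial was powered on. All of that stands.

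The visit set is also an inference. SAP Appendix 1 puts the Day 5 analysis and the analysis of the other days in separate rows, so two fits are possible, and the loss nearly vanishes if the primary fit stops at Day 10. This stands as a condition. It does not settle which visits are fitted, and that gap is half of the point.

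The size is soft. The grid starts at 85% at the floor by Day 34 and so leaves out lighter cases, where the loss is close to nil. The baseline inputs lean on 7 patients. The shares of the grid are counts of assumption sets, not probabilities.

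The floor-imputation sentence directly follows the mITT1 sentence. The calculation applies it to both sets, which is an assumption. The mechanism needs only that floor samples take nearly constant values.

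Limiting the primary fit to Days 3 and 5 recovered the same Day 5 precision in the separate simulation. That is a fair alternative, but it gives up later data on participants whose Day 5 swab is missing.

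**Conclusion.** The point holds as an efficiency improvement to a valid analysis. It shows no material bias, no type I error inflation and no fault in the stated sample size. Two facts are firm: there is no baseline-by-visit term, and the visits in the fit are not named.

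The cost depends on how the second gap is filled. Through Day 10 it is negligible. Through Day 34 it ranges from almost nothing with a light floor to several points of power, and above 10 points in the least favourable sets with a heavy floor.

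Whether planned power survives depends on what 1.8 represents, which SAP 2.4 does not say. If it is the raw SD, 90% is kept while the common slope is at most twice the Day 5 slope. If it is already baseline-adjusted, power as written over the grid is 0.76 to 0.89 (median 0.86) against the planned 0.90. Confidence in the mechanism is high. Confidence in the size is moderate, because baseline SD, visit slopes and floor shares are all assumed.

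**What to change.** Add a baseline viral RNA-by-visit interaction to the model in SAP 6.1.1 and Protocol 9.3.2.2, and state in one sentence which visits enter the primary fit. Keep the later visits, since they carry information on participants with partial data. Carry the term into SAP 6.3.4 and 6.3.8, which reuse the model. For plasma this is for consistency only; no calculation was made there.

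The cost is one model term, which means six extra slopes if seven visits are fitted, and no new data. Protocol 9 says that "any major modifications of the primary endpoint definitions or their analyses will also be reflected in a protocol amendment", so the sponsor must decide whether this change counts as major. It must be settled before unblinding.

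### The mITT1 model that gates both key secondary endpoints fits one baseline RNA slope to all visits and to RNA-negative participants; visit-specific baseline terms would recover some Day 5 precision at almost no cost

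*SAP*

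**What the plan says.** SAP Section 4 defines two efficacy sets. The mITT set requires baseline swab RNA of at least 2.0 log10 copies/mL. The mITT1 set requires a dose and a positive baseline rapid antigen test, with no RNA condition. SAP 2.4 plans for RNA-negatives: "Assuming approximately 10% of participants will have a negative viral RNA result at baseline".

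SAP 6.1.1 gives one model, an MMRM with unstructured covariance: "The analysis will include the fixed effects of treatment, geographic region, baseline viral RNA level, visit, and treatment-by-visit interaction". Treatment is crossed with visit; baseline is not. The same section adds "The secondary analysis for primary endpoint will be performed using the mITT1 analysis set", without changing the model, and sets results below LLOQ to 1.7 and undetectable results to 0.0. SAP 6.1.2 lists only a per-protocol supplementary analysis.

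Under SAP 5.1, once the mITT test is positive, "the secondary analysis for the primary efficacy endpoint using the mITT1 analysis set will be tested". Only if that is positive are the two key secondary endpoints tested, by Hochberg. Protocol 9.1.2 and 9.3.2.2 agree.

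The SAP does not call the baseline term linear. That is the natural reading, because SAP 6.2.1 writes out categories of baseline viral load (below 4, 4 or more) where it wants them.

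**The concern.** Two features of the baseline term can misfit Day 5.

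- **One slope for all visits.** The outcome is change from baseline. By late visits most participants are likely to be near the assay floor, so change is close to minus the baseline value. At Day 5 the relation is likely to be shallower. A single coefficient averages over these and leaves avoidable residual variance at Day 5. This applies to mITT as well.
- **One line for all participants.** An undetectable baseline enters at 0.0, which is 2.0 log10 below the lowest value possible in mITT. If an antigen-positive, RNA-negative result reflects a poor swab, Day 5 RNA need not lie on the line extrapolated from the positives. This is specific to mITT1.

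The mITT1 test stands in front of both key secondary endpoints, so a wider standard error there lowers the chance that either is formally tested.

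**Working it through.** **1. The plan's own figures.** Inputs from SAP 2.4: "Assuming a SD of 1.8 (based on EPIC-HR, NCT04960202"; "210 participants in nirmatrelvir/ritonavir group and 105 participants in placebo/ritonavir group"; "is expected to provide 90% power to detect a difference of 0.7" log10; "between groups using a 2-sided 0.05 alpha level test".

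SE = 1.8 × √(1/210 + 1/105) = 0.2151. Power = Φ(0.7/0.2151 − 1.960) = Φ(1.294) = 90.2%. Randomized: 315/(0.90 × 0.85) = 411.8, against 411 stated. Both reproduce.

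If all 411 are antigen-positive at baseline, evaluable mITT1 is 411 × 0.85 = 349, of whom about 35 are RNA-negative.

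**2. Misfit of a single line at Day 5 alone.** Let p be the RNA-negative share, g their mean Day 5 distance from the line fitted to the positives, r the correlation of RNA-negative status with baseline, and s the residual SD. Then

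residual variance = s² + p(1 − p)(1 − r²)g².

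Assumed: positives have baseline mean 5.0 and SD 1.5; half the negatives are at 0.0 and half at 1.7 (mean 0.85, SD 0.85). Then p(1 − p)d² = 0.09 × 4.15² = 1.550. The within-group variance is 0.9 × 1.5² + 0.1 × 0.85² = 2.097. So r² = 1.550/3.647 = 0.425. With s = 1.8:

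- g = 1: √(1 + 0.0518/3.24) gives an SE 0.8% larger
- g = 2: √(1 + 0.207/3.24) gives 3.1%
- g = 3: √(1 + 0.466/3.24) gives 6.9%

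Varying the baseline mean (4.5–6.1) and SD (1.2–1.5) gives 0.5–0.9%, 2.0–3.5% and 4.4–7.7%. At g = 0 the increase is nil.

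**3. Dilution, for scale.** At N = 349, SE = 1.8 × √(1/232.7 + 1/116.3) = 0.2044. An undiluted 0.7 has power Φ(0.7/0.2044 − 1.960) = 92.9%. With no effect in the 10% negatives, the effect is 0.9 × 0.7 = 0.63 and power is 86.9%. The line misfit then takes it to 86.4%, 84.8% and 82.2% at g = 1, 2 and 3.

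**4. The SAP's MMRM.** Step 2 describes a Day 5 ANCOVA. The SAP model was simulated with 349 participants 2:1, 10% negative, all seven post-baseline visits, complete data, 1.7/0.0 coding and 200 runs per scenario. The Day 5 slope on baseline was 0.5, 0.6 and 0.4 for baseline means 5.0, 6.1 and 4.5. Entries are mean model SEs at Day 5.

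| Baseline mean; negatives at Day 5 | g | SAP model | + shared indicator | Baseline-by-visit | Baseline-by-visit + indicator-by-visit |
|---|---|---|---|---|---|
| 5.0; intermediate | 0.73 | 0.1925 | 0.1920 | 0.1779 | 0.1774 (−7.8%) |
| 5.0; like positives | 1.93 | 0.1914 | 0.1902 | 0.1852 | 0.1796 (−6.2%) |
| 6.1; stay low | 0.59 | 0.2080 | 0.2080 | 0.1883 | 0.1884 (−9.4%) |
| 6.1; intermediate | 1.12 | 0.2062 | 0.2056 | 0.1912 | 0.1906 (−7.6%) |
| 6.1; like positives | 3.00 | 0.2053 | 0.2027 | 0.2021 | 0.1941 (−5.5%) |
| 4.5; stay low | −0.73 | 0.1892 | 0.1892 | 0.1720 | 0.1711 (−9.6%) |
| 4.5; intermediate | −0.15 | 0.1870 | 0.1871 | 0.1740 | 0.1742 (−6.8%) |
| 4.5; like positives | 1.46 | 0.1843 | 0.1831 | 0.1800 | 0.1766 (−4.2%) |

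The shared indicator does at best 1.3% here (0.2053 to 0.2027), because its coefficient, like the slope, is averaged over visits. Baseline-by-visit supplies most of the gain, except where negatives behave like positives. In the 6.1 case it gives 1.6% alone and 5.5% with the indicator by visit.

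Runs over other assumed trajectories widened the range for the full visit-specific form to about 1–11%, never worse than the SAP model. They widened the range for the shared indicator to 0–5%, usually under 1%. One small set (60 runs per scenario) showed up to 22% from baseline-by-visit alone; I do not rely on it.

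**5. What 1–11% could mean.** Take 0.2044 as the SAP-model SE and 0.63 as the effect. A 1% cut gives Φ(0.63/0.2023 − 1.960) = 87.6%, and an 11% cut gives Φ(0.63/0.1819 − 1.960) = 93.4%, against 86.9%.

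**The case against.** The strongest reply is that nothing is shown to be lost. The documents give no Day 5 level for RNA-negatives and no baseline-to-Day 5 slope. If negatives sit near the line, their coding costs nothing: with baseline mean 5.0, negatives staying low and g = 0.14, the Day 5 ANCOVA SE was 0.1742 without an indicator and 0.1745 with one. That stands, so the point is conditional.

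Second, the gate is reached only after mITT succeeds, and the two sets share about 90% of participants. What matters is the probability that both tests pass. For a shared indicator, simulation moved that by −0.8 to +1.7 points, usually 0. This also stands: the power figures in step 5 are for mITT1 alone and overstate the effect on the sequence.

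Third, a reader might infer that mITT1 is the less precise analysis. The results do not support that. In every MMRM scenario the SAP-form SE was smaller in mITT1 than in mITT (for example 0.1925 against 0.2020), because mITT1 is larger and its negatives vary less.

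The reply does not reach the visit-specific form, which helped in every scenario and uses only data already collected.

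**Conclusion.** The structure is in the documents: a gate on the secondary family, about 10% RNA-negatives coded 0.0 or 1.7, and one baseline coefficient for all visits and participants. This can lose Day 5 precision. Under the assumed trajectories, visit-specific terms recover about 1–11% of the standard error. This is an optional efficiency gain and not a defect in validity.

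Three stronger readings are tempting and unsupported:

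- **Biased treatment effect or inflated type I error.** Randomization protects the comparison whatever the shape of the baseline relation.
- **Certain SE inflation from the RNA-negatives.** It follows only if they lie well off the line, visibly from about 2 log10, and the documents are silent on this.
- **One below-LLOQ indicator removes the loss.** That holds approximately for a Day 5 ANCOVA, not for the SAP's MMRM.

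No version restores dilution, which costs about 6 points of power (92.9% to 86.9%) if RNA-negatives have no effect to show.

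The sizes assume baseline means of 4.5–6.1 and slopes of 0.4–0.6 in the tabled runs, seven visits in the MMRM and no missing data.

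**What to change.** Before unblinding, in SAP 6.1.1 and for the mITT1 analysis, replace the single baseline RNA term with baseline-by-visit and add baseline below LLOQ (yes/no) by visit. State that the 1.7 and 0.0 values apply to baseline as well as later samples, and name the visits in the model.

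Baseline-by-visit is worth considering for mITT too, since the shared slope is not peculiar to mITT1. Protocol Section 9 requires a protocol amendment for major changes to the primary endpoint analyses, so the sponsor should decide whether that extension needs one. SAP 2.1, which now lists no departures from the protocol, would need an entry.

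The cost is one SAP line and, with seven visits, six extra slope parameters and seven indicator parameters in a model of about 349 participants. No new data are needed. The sponsor should specify a fallback, such as baseline-by-visit alone, in case very few participants are below LLOQ at baseline.
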